### **3.2.7.2 *Pregnancy***

If a patient becomes pregnant during treatment or within 1 month following the last dose of the study drug, administration (if still ongoing) must be discontinued and the sponsor is notified within 24 hours of investigator awareness of the pregnancy. For the purposes of this study, pregnancy of any patient will be considered an AE but not, in itself, an SAE, and should be reported to the sponsor on a pregnancy form rather than an SAE form. However, if pregnancy leads to an SAE for example, a spontaneous abortion or miscarriage resulting in medical hospitalization, an SAE form should be completed. Every attempt must be made to follow the pregnancy to resolution, which includes birth or termination of the pregnancy. If the information is available, the resolution must be reported to the sponsor on a pregnancy form. If possible, births should be followed by the investigator for 8 weeks for observation of any congenital abnormalities, and any such abnormalities should be reported within 24 hours of investigator awareness of the observation to the sponsor.

Pregnancy of a male patient's partner will not be considered an AE, and the male patient should not be withdrawn from the study. If a male patient's partner becomes pregnant during the specified time period (from first dose until 3 months after the last dose), the investigator will inform the sponsor within 24 hours of investigator awareness of the pregnancy, as well as the IRB, as appropriate, and will provide appropriate medical follow-up, if agreed to by the partner.

### **3.2.7.3 *Overdose***

Overdose is defined as administration to the patient of a dose of test article that exceeds by more than 40 mg/dose or 80 mg/week.

Any overdose of HBI-8000 should be reported via an SAE form within 24 hours of investigator awareness of the overdose to the sponsor, regardless of association with an AE. In the case that the overdose did not result in an AE, the investigator should report this as "overdose, no AE" on the SAE form and specify the intended amount, as well as the actual amount, of drug administered.

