## **1.6 Clinical Studies**

To date, more than 300 patients have been dosed with HBI-8000/chidamide in clinical trials. Over 1000 patients have been prescribed chidamide (Epidaza) in China since marketing approval was granted in December 2014.

Clinical trials with HBI-8000 have shown that HBI-8000 is generally well tolerated in patients with advanced solid tumors or relapsed or refractory lymphoma at doses up to 32.5 mg TIW and 50 mg BIW administered continuously with or without intermittent breaks (total weekly doses of approximately 100 mg in Phase 1 trials). The Phase 2 registration study in PTCL conducted in China demonstrated significant efficacy, with the best response rate of 28% (22/79) and a good safety profile. A subgroup analysis of the various histological subtypes revealed that the ORR was as high as 44 to 50% [Shi 2013, Shi 2015]. Based on these data the CFDA granted conditional approval on 23 December 2014 for the use of chidamide (HBI-8000) for the treatment of relapsed or refractory PTCL.

In Japan, pharmaceutical and medical devices agency (PMDA) was consulted in 2013 to obtain advice for the clinical development of HBI-8000 for relapsed or refractory PTCL and ATL in Japan. For a Phase 2 dose selection, a Phase 1 study (HBI-8000-201) in patients with relapsed or refractory NHL including PTCL and ATL was initiated in Japan in April 2014 and has now completed. Phase 2 clinical trials are planned in patients with relapsed or refractory ATL and relapsed or refractory PTCL.

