### **2.6.8 Management and Dosage Modifications for Unacceptable Hematologic and Non-hematologic Adverse Events**

National Cancer Institute Common Terminology Criteria for Adverse Events (NCI CTCAE) version 4.03 will be used to grade the severity of toxicities. An unacceptable toxicity is defined as the following treatment-related AEs:

- Grade 4 afebrile neutropenia >7 days despite optimal growth factor support
- Grade  $\geq 3$  febrile neutropenia or neutropenic infection
- Grade  $\geq 3$  thrombocytopenia with clinically significant bleeding or Grade  $\geq 3$  thrombocytopenia requiring a platelet transfusion
- Grade  $\geq 3$  nausea, vomiting, diarrhea, or electrolyte imbalances lasting greater than 48 hours despite optimal prophylactic and curative treatment
- Grade  $\geq 3$  allergic reaction
- Grade  $\geq 3$  other non-hematologic AEs
- Treatment delay >14 days secondary to recovery from study drugs- related AEs

**Table 1** summarizes the guidelines for dosage adjustment in the event of unacceptable AEs. Two dose reductions are allowed (from 40 mg to 30mg, or from 30 mg to 20 mg). If unacceptable AEs recur despite 2 dose reductions, the study treatment will be permanently discontinued and post-treatment follow-up ensues. However, if the patients are having clinical benefit, further treatment may be considered after discussion with the sponsor. In the event of AE, such as hematological AE-uncomplicated, necessitating 2 treatment interruptions, dose will be reduced when treatment resumes. However, if strongly needed for patient safety, dose can be reduced according to the investigator judgement, even if unacceptable hematological AE-uncomplicated is occurred once.

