## **2.7 Study Drug Administration**

During this the trial, patients will receive 40 mg of HBI-8000 administered approximately 30 minutes after any regular meal as four 10 mg tablets BIW continuously. The dosing interval would be 3 to 4 days for a total of 80 mg over 7 days. At each visit when study medication is dispensed, the study site staff will contact the Interactive Web Response System (IWRS) before dispensing.

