## **3.2.8 *Follow-Up of Adverse Events***

Patients should be asked to specifically describe any signs, symptoms, or AEs (regardless of relationship to therapy) they may notice prior to the start of the study or thereafter. At a minimum, patients should be asked to report AEs at each visit to the study site. Conditions that the patient experienced prior to informed consent should be recorded in the medical history section of the eCRF.

Follow-up of an "overdose" should include continued monitoring of all protocol-specific laboratory results, including chemistry and hematology, using the protocol-specified

time points for laboratory tests, with the exception that an additional full series of chemistry, hematology, and coagulation tests, a full physical examination, vital signs, and ECG should be conducted within 24 hours of investigator awareness of that the patient received an “overdose”. Following this additional ad hoc re-evaluation, the investigator should use his or her medical judgment in deciding whether additional supplemental medical treatment is needed to treat adverse medical consequences of the overdose. Also after the ad hoc re-evaluation, the investigator should use his or her medical judgment in deciding whether additional supplemental monitoring is needed to track resolution of any AEs or other abnormal findings to the point of resolution to a CTCAE Grade 1 AE.

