### **3.2.10 Vital Signs, Physical Findings and Other Safety Assessments**

Vital signs measurements will include pulse rate and systolic and diastolic blood pressure in a seated position of at least 5 minutes.

Physical examinations will be performed. A skin assessment will be conducted per the standard procedure of the site. For skin lesions, photograph with an adjacent ruler to indicate size will be obtained, if needed.

ECG for safety are to be 12-lead. Vital signs measurements should be performed prior to the ECG.

To assess QTc intervals, 12-lead ECGs in triplicate will be obtained at pre-dose and  $3.5 \pm 0.5$  hours after taking study medications on C1D1 and C2D1. The patient should be in seating position for 5 minutes before the first ECG is obtained, followed by second and third ECGs with  $5 \pm 2$  minutes between ECG measurements.

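### Section 3.2.7.3 names no reference amount for overdose and ignores dose reductions, so a doubled dose at the 20 mg level is not an overdose on any reading

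*Combined protocol and SAP*

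**What the plan says.** All references are to the combined protocol and SAP.

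- Section 3.2.7.3 defines overdose as "a dose of test article that exceeds by more than 40 mg/dose or 80 mg/week". The thing exceeded is not named. Sections 3.2.1.2 and 3.2.8 add reporting and follow-up duties but no definition.
- Section 3.2.7.3 adds that any overdose "should be reported via an SAE form within 24 hours of investigator awareness of the overdose", with or without an AE, and that the form must give the intended and the actual amount.
- Section 3.2.8 requires that, after an overdose, "an additional full series of chemistry, hematology, and coagulation tests, a full physical examination, vital signs, and ECG should be conducted within 24 hours".
- Section 2.7 sets the plan at 40 mg per dose, as four 10 mg tablets twice a week: "The dosing interval would be 3 to 4 days for a total of 80 mg over 7 days".
- Section 2.6.8 and Table 1 set two lower levels: "Two dose reductions are allowed (from 40 mg to 30mg, or from 30 mg to 20 mg".
- Section 2.11 separately defines non-compliance by amount (under 75% or over 125% in a cycle) and by interval (more than two gaps under 3 days in a cycle). Its stated consequences are counselling and, if the patient cannot follow instructions, discontinuation.

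**The concern.** The two numbers in the definition equal the full planned dose and the full planned weekly total. That suggests ceilings: more than 40 mg at once, or more than 80 mg in a week. The verb phrase, however, describes an amount over something else, and the request for intended and actual amounts fits that sense. The two senses put the trigger at different places.

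More important, the limits are fixed numbers while the prescribed dose is not. After two reductions the patient takes 20 mg, and the limits stay where they were. Patients reach that level because 40 mg and then 30 mg led to unacceptable toxicity, so they are the patients for whom a dosing error should most readily prompt a laboratory check and an ECG.

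What is at stake is safety reporting and work-up. The overdose definition is the only thing that triggers the 24-hour form and the extra 24-hour assessments. The synopsis plans about 22 patients at 25 to 35 sites, fewer patients than sites, so a shared convention is unlikely to form without clear text.

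**Working it through.** **Plan.** 4 × 10 mg = 40 mg per dose; 2 × 40 mg = 80 mg per 7 days. This reproduces section 2.7. With gaps alternating between 3 and 4 days (days 1, 4, 8, 11, ...), no 7-day window holds more than two doses.

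**Two readings.** Ceiling: actual dose above 40 mg, or weekly total above 80 mg. Excess: actual minus prescribed above 40 mg per dose, or above 80 mg per week.

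| Prescribed dose | Ceiling: dose / week above | Excess: dose / week above | Trigger ÷ prescribed dose, ceiling vs excess |
|---|---|---|---|
| 40 mg | 40 / 80 mg | 40+40 = 80 / 80+80 = 160 mg | 1.0 vs 2.0 |
| 30 mg | 40 / 80 mg | 30+40 = 70 / 60+80 = 140 mg | 1.33 vs 2.33 |
| 20 mg | 40 / 80 mg | 20+40 = 60 / 40+80 = 120 mg | 2.0 vs 3.0 |

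If the excess were measured from the unreduced 40 mg and 80 mg, the limits at the reduced levels would be higher still (80 and 160 mg).

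**One doubled dose, with the other dose of the week as prescribed.**

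| Level | Dose / week | Ceiling | Excess |
|---|---|---|---|
| 40 mg | 80 / 120 mg | overdose | no: 40 and 40 over |
| 30 mg | 60 / 90 mg | overdose | no: 30 and 30 over |
| 20 mg | 40 / 60 mg | no: 40 is not above 40, 60 is not above 80 | no: 20 and 20 over |

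**Both doses of the week doubled.** At 20 mg the week totals 80 mg: not above 80 (ceiling), and 80 − 40 = 40, not above 80 (excess). At 40 mg the week totals 160 mg: an overdose on the ceiling reading; on the excess reading 160 − 80 = 80, not above 80.

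Because tablets are 10 mg, the smallest reportable single dose for a patient on 20 mg is 50 mg on the ceiling reading and 70 mg on the excess reading: five or seven tablets instead of two.

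**Does section 2.11 catch it?** Take the cycle base as eight prescribed doses, which 2.11 does not state. At 20 mg, 8 × 20 = 160 mg. One doubled dose gives 180/160 = 112.5%, and two give 200/160 = 125%, which is not over 125%. A third gives 220/160 = 137.5% and is flagged, but as non-compliance, not as an overdose.

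**Meaning of a week.** On the ceiling reading, doses on days 22, 25 and 28 total 3 × 40 = 120 mg in 7 days, above 80. Both gaps are 3 days. Day 28 lies inside the ±4 day window of the Cycle 2 Day 1 visit (Table 4), a visit at which "12-lead ECGs in triplicate will be obtained at pre-dose and" about 3.5 hours after the dose. The text does not say whether a week is rolling or fixed, so whether this is an overdose depends on where weeks are taken to start. At 30 mg the total is 90 mg, also above 80; at 20 mg it is 60 mg and is not flagged.

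**The case against.** The strongest reply is that the ceiling reading is plainly intended. The limits match section 2.7 exactly, and on that reading every doubled dose at 40 mg and at 30 mg is reported. That stands. A reader might infer that the plan lets an 80 mg dose go unreported, at 80/50 = 1.6 times the upper BIW dose in section 1.6, which describes tolerability "at doses up to 32.5 mg TIW and 50 mg BIW administered continuously". The documents do not support that as the main finding: it needs the less plausible reading, and section 1.5.1 reports a less than proportional rise in exposure with dose, so 1.6 is a ratio of doses and not of exposures.

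A reader might also infer that the plan turns permitted dosing into a serious-event report. That too goes further than the text. Three doses in 7 days satisfy the 3 to 4 day interval but break the 80 mg over 7 days in the same sentence of section 2.7. The visit window also contains planned dosing days 25, 29 and 32, so day 28 is avoidable. What remains is an extra form and an extra set of tests.

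On the 20 mg level, the reply is that 40 mg is only the trial's starting dose, that all AEs are collected under section 3.2.2 whatever the definition says, and that drug logs and tablet counts continue. These safeguards are real, and the investigator may order tests at any time. They do not replace the definition: none of them requires the 24-hour form or work-up, and a starting dose is little reassurance in a patient who has since been reduced twice.

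**Conclusion.** The point holds, chiefly for the reduced dose. At 20 mg, a doubled dose or a doubled week is not an overdose on either reading, and this does not depend on how a week is defined. The trigger lies above 2.0 or 3.0 times the prescribed dose, against 1.0 or 2.0 times at the 40 mg level.

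Two ambiguities are secondary. At 40 mg the literal words double the trigger from 40 to 80 mg per dose and from 80 to 160 mg per week, although the lower figures are the likelier intent. An undefined week allows over-reporting of two consecutive 3-day gaps at the 40 and 30 mg levels.

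The documents do not say how many patients will reach 20 mg or how often doses are doubled or taken early, so no frequency is claimed. It would be wrong to infer any effect on the efficacy results: ORR, FAS and PPS do not use the overdose definition. Nor do sections 2.11 and 3.2.7.3 conflict; 2.11 has a different purpose and merely provides no numeric backstop. This is a safety-reporting defect that should be corrected.

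**What to change.** Replace the definition in section 3.2.7.3 with:

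> Overdose is defined as more than the currently prescribed dose (40 mg, or 30 mg or 20 mg after a Table 1 reduction) taken within any 24 hours, or more than twice the currently prescribed dose in any 7 consecutive days, unless each of those doses was taken at least 3 days after the one before.

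State that the exception belongs to the 7-day limit only. The text then reports a doubled dose at all three levels, two full doses on one day with the next one skipped (80 mg in 24 hours at the 40 mg level), and a third dose in 7 days after a gap under 3 days. It does not report the day 22, 25, 28 pattern.

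The cost is one sentence by amendment. No new data are needed, because the drug log in section 2.11 already records dates and times. There are two downsides. There will be a few more overdose reports at the reduced levels. A third dose in 7 days at 3-day gaps will go unreported: that is 120 mg in the week at the 40 mg level, 1.2 times the "total weekly doses of approximately 100 mg in Phase 1 trials" of section 1.6. Dosing every 3 days throughout would average 40 × 7/3 = 93.3 mg per week, 117% of plan and below that total.

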## **3.2.8 *Follow-Up of Adverse Events***

Patients should be asked to specifically describe any signs, symptoms, or AEs (regardless of relationship to therapy) they may notice prior to the start of the study or thereafter. At a minimum, patients should be asked to report AEs at each visit to the study site. Conditions that the patient experienced prior to informed consent should be recorded in the medical history section of the eCRF.

Follow-up of an "overdose" should include continued monitoring of all protocol-specific laboratory results, including chemistry and hematology, using the protocol-specified

time points for laboratory tests, with the exception that an additional full series of chemistry, hematology, and coagulation tests, a full physical examination, vital signs, and ECG should be conducted within 24 hours of investigator awareness of that the patient received an “overdose”. Following this additional ad hoc re-evaluation, the investigator should use his or her medical judgment in deciding whether additional supplemental medical treatment is needed to treat adverse medical consequences of the overdose. Also after the ad hoc re-evaluation, the investigator should use his or her medical judgment in deciding whether additional supplemental monitoring is needed to track resolution of any AEs or other abnormal findings to the point of resolution to a CTCAE Grade 1 AE.

### **3.2.9 Clinical Laboratory Evaluations**

Clinical laboratory tests, fasting or post-meal, will be reviewed for results of potential clinical significance at all time points throughout the study. The abnormality will be graded under Investigation category of CTCAE version 4.03 independent of clinical significance. The investigator will evaluate any change in laboratory values.

Hematology testing will include the following parameters: hemoglobin, hematocrit, red blood cell count, white blood cell count with differential, platelet count, coagulation, including prothrombin time, activated partial thromboplastin time, and international normalized ratio. Serum chemistry testing will include the following parameters: blood urea nitrogen, creatinine, AST, ALT, gamma-glutamyl transpeptidase, total bilirubin (including direct fraction if total bilirubin is abnormal), lipase, amylase, total protein, albumin, alkaline phosphatase, sodium, potassium, calcium, magnesium, random blood glucose, LDH, creatine kinase MB fraction.

Urinalysis (glucose, protein, occult blood) will be performed by dipstick method, and in the event of abnormal dipstick results, additional test may be required.

The following information will be captured for blood sample collection in each patient's eCRF:

- Subject number.
- Time and date of dose administration
- Time and date of patient's most recent ingestion of food prior to dose administration.

### **3.2.10 Vital Signs, Physical Findings and Other Safety Assessments**

Vital signs measurements will include pulse rate and systolic and diastolic blood pressure in a seated position of at least 5 minutes.

Physical examinations will be performed. A skin assessment will be conducted per the standard procedure of the site. For skin lesions, photograph with an adjacent ruler to indicate size will be obtained, if needed.

ECG for safety are to be 12-lead. Vital signs measurements should be performed prior to the ECG.

To assess QTc intervals, 12-lead ECGs in triplicate will be obtained at pre-dose and  $3.5 \pm 0.5$  hours after taking study medications on C1D1 and C2D1. The patient should be in seating position for 5 minutes before the first ECG is obtained, followed by second and third ECGs with  $5 \pm 2$  minutes between ECG measurements.

### 3.3 Blood Volume

The total blood volume for each patient to be collected at screening is approximately 20 mL. Blood volume collected for safety tests on Days 1, 8, 15, and 22 of Cycle 1 will be approximately 30 mL. The sum of Screening and Cycle 1 is shown in Table 2. Assuming each patient would receive up to 6 Cycles of treatment, subsequent cycles will have blood collections for safety tests on Day 1 and 15 of Cycle 2 then Day 1 of Cycles 3 to 6. The total blood collection volume for Cycles 2 to 6 will be approximately 60 mL (Table 3). For patients receiving treatment Cycle 7 and beyond, 10.5 mL blood will be drawn for safety tests. The total blood collection volume for EoT will be approximately 6 mL for safety tests.

**Table 2: Screening-Cycle 1**

	Number of Samples	Sample Volume (mL)	Total Volume (mL)
Hematology	5	2	10
Serum chemistry	5	4	20
Coagulation	3	4.5	13.5
HTLV-1 antibodies	1	1	1
Hepatitis B virus tests	1	2	2
Hepatitis C virus tests	1	4	4
Total			50.5

**Table 3: Cycle 2-Cycle 6**

	Number of Samples	Sample Volume (mL)	Total Volume (mL)
Hematology	6	2	12
Serum chemistry	6	4	24
Coagulation	5	4.5	22.5
Total			58.5

## **3.4 Independent Review**

### **3.4.1 Data Safety Monitoring Board**

A DSMB has been established to monitor the safety observed during the conduct of this study. For all patients, weekly safety laboratory tests should be obtained during the first 28 days and closely monitored for safety signals, especially the neutropenia and transaminase elevation. DSMB consists of 3 oncologists who are experienced in treating patients with ATL and are not associated with this study. They are assisted by 1 DSMB statistician.

DSMB convenes at planned intervals based on patient accrual (see [Section 2.6](#)). Upon reviewing cumulative safety data from the study and taking into consideration of state-of-the-art medical practice, they will advise sponsor for treatment modification including dose adjustment, AE management, and continuation of treatment.

### **3.4.2 Independent Radiology Review**

To ensure consistent radiology method is applied to assess disease response cross the entire study, designated radiologists will review sequential imaging studies of individual patients. They will assign response outcome including best response, dates of initial response and progression when applicable, based on Tsukasaki Criteria. They will be blinded to the local radiology findings. Should discrepancy between assessments by independent radiologist (s) and site occur, a second independent radiologist will adjudicate by selecting assessment from either site or first independent radiologist for final analysis.

### **3.4.3 Independent Overall Efficacy Review**

To ensure consistent overall efficacy determination, designated independent oncologists will review sequential clinical data of individual patients including radiological assessment provided by the independent radiological review. They will assign response outcome including best response, dates of initial response and progression when applicable, based on Tsukasaki Criteria.

## **4.0 QALITY CONTROL AND QALITY ASSURANCE**

According to the Guidelines of Good Clinical Practice (GCP) (CPMP/ICH/135/95), the sponsor is responsible for implementing and maintaining quality assurance and quality control systems with written Standard Operating Procedures (SOPs).

Quality control will be applied to each stage of data handling.

The following steps will be taken to ensure the accuracy, consistency, completeness, and reliability of the data:

- Clinical laboratory parameters
- Study site initiation visit
- Early site visits post-enrollment
- Routine site monitoring
- Ongoing site communication and training
- Data management quality control checks
- Continuous data acquisition and cleaning
- Internal review of data
- Quality control check of the clinical study report (CSR)

In addition, sponsor may conduct periodic audits of the study processes, including, but not limited to study site, site visits, clinical laboratories, vendors, clinical database, and final CSR. When audits are conducted, access must be authorized for all study-related documents including medical history and concomitant medication documentation to authorized sponsor's representatives and regulatory authorities.

